Another abnormality well documented in cirrhotic patients, more frequently in patients with advanced disease, is spur cell anemia. Although first described in alcoholic cirrhosis, it is seen in all etiologies and is a poor prognostic marker. A spur cell burden of $\geq 5\%$ was found to be associated with a 67% 90-day mortality rate in a recent study¹¹. Furthermore, patients with spur cell anemia have decreased red blood cell (RBC) lifespan and are transfusion resistant as transfused RBCs quickly acquire the pathologic morphology. Spur cells are thought to occur secondary to red cell membrane abnormalities secondary to altered cholesterol composition, similar to the abnormal erythrocyte rigidity rheologic property described above. Interestingly, the lecithin-cholesterol acetyltransferase enzyme has been investigated as a potential key factor in spur cell anemia. A 1972 study by Cooper et al¹² measured LCAT enzyme activity by way of a surrogate method involving change in serum free cholesterol after 6-hour incubation. Lower levels of LCAT were found in patients with spur cells compared to normal controls; however, there was only a weak association with red cell lipid content.

Furthermore, platelet dysfunction in cirrhosis has also been tied to lipid abnormalities. A review of dyslipidemia in liver disease by Miller noted that platelets, similar to erythrocytes, have an imbalanced cholesterol to phospholipid ratio and associated impaired aggregation¹³. Thus, the deficient primary hemostasis noted in cirrhotic patients may not be just a function of

thrombocytopenia itself but also an intrinsic abnormality of platelet function related to a disruption in normal cholesterol pathways.

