Subjects will be classified as adrenally sufficient or insufficient on the basis of standard-dose cortisol stimulation test. Variables of interest for comparison between the groups include MELD score, Child-Turcotte-Pugh (CTP) classification, high-density lipoprotein (HDL) levels, presence of spur cell anemia, serum cholesterol ester percentage (surrogate for LCAT enzymatic activity), cortisol binding globulin levels, and free cortisol levels. Student's t-test and Chi Square tests will be utilized to determine significance; a p-value <0.05 will be used as our threshold for significance. If multiple factors are found to be significantly different in a univariate fashion between classification groups, a multivariate logistic regression analysis will be performed for adjusted analysis. We will also seek to define any correlations between variables. Furthermore, we will assess correlation between MELD score and serum cholesterol ester percentage, spur cell anemia, HDL levels, cortisol binding globulin levels, and free cortisol levels; similar correlate analysis will be done using CTP classification instead of MELD score.

Prevalence of adrenal insufficiency (AI) in cirrhosis varies widely based on several factors, including severity of liver disease (i.e. MELD score or CTP classification) and the testing modality used to assess for AI. Given that admitted patients to UVA are typically CTP B or C, we expect the incidence to be about 33%. Thus, 120 patients recruited should be sufficient to provide a statistical difference in our outcome measures of interest, assuming a 20% dropout rate to lead to 100 patients completing study protocol.

3. Provide a justification for the sample size used in this protocol.

Answer/Response:

Given that admitted patients to UVA are typically CTP B or C, we expect the incidence of adrenal insufficiency to be about 33%. We feel 100 patients would be adequate to complete a pilot study to test for correlation between adrenal insufficiency, low serum cholesterol ester percentage, and spur cell anemia. There is no current literature upon which to do a formal power calculation (although low levels of cholesterol esterification is a well-established near-universal metabolic finding in cirrhotic patients), but this sample size would allow for adequate size comparator groups and decrease the likelihood of a Type II statistical error.

4. What is your plan for primary variable analysis?

Answer/Response:

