Our primary outcome of interest is comparing prevalence of cholesterol esterification deficiency and spur cell anemia in cirrhotic patients with and without adrenal insufficiency.

5. What is your plan for secondary variable analysis?

Answer/Response:

- Demonstrate association between deficiency in cholesterol esterification and presence of spur cell anemia

- Demonstrate association between deficiency in cholesterol esterification and low HDL levels
- Correlate higher MELD score with presence of adrenal insufficiency
- Correlate higher MELD score with presence of spur cell anemia
- Correlate higher MELD score with lower HDL levels
- Correlate higher MELD score with deficiency in cholesterol esterification
- Correlate higher CTP classification with presence of adrenal insufficiency
- Correlate higher CTP classification with presence of spur cell anemia
- Correlate higher CTP classification with lower HDL levels
- Correlate higher CTP classification with deficiency in cholesterol esterification
- Correlate lower cortisol binding globulin levels with higher MELD score and CTP classification
- Correlate lower cortisol binding globulin levels with adrenal insufficiency
- Correlate lower free cortisol levels with higher MELD score and CTP classification
- Correlate lower free cortisol levels with adrenal insufficiency
- Multivariate logistic regression if several variables are found to be significant

6. Have you been working with a statistician in designing this protocol?

Answer/Response: No

IF YES, what is their name?

Answer/Response: N/A

7. Will data from multiple sites be combined during analysis?

Answer/Response: No

7(a). Does the study involve randomization?

Answer/Response: No

IF YES, will randomization be done at each site or among sites?

Answer/Response: N/A

7(b). Has the sample size calculation considered the variation among sites?

Answer/Response: N/A

7(c). When combining the data from multiple sites to assess the study results, is the effect of the treatment to be tested (or the association to be tested) assumed to be the same across sites or vary among sites? What is the modelling strategy?

Answer/Response: N/A

7(d). Is there a common protocol used in all sites?

Answer/Response: N/A

IF NO, how will differences among sites, such as those related to the implementation, inclusion criteria, patient characteristics, or other sites characteristics, be considered to assess the study results?

Answer/Response: N/A

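### A severity-adjusted estimate of the primary association with adrenal insufficiency is not guaranteed, because the only adjusted model depends on univariate significance and its terms are not stated

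*Combined protocol and SAP*

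**What the plan says.** Statistical Considerations, item 4, defines the primary analysis: "Our primary outcome of interest is comparing prevalence of cholesterol esterification deficiency and spur cell anemia in cirrhotic patients with and without adrenal insufficiency". It names no covariate. Item 2 supplies the tests (t-test and chi-square at 0.05) and the only route to adjustment: "If multiple factors are found to be significantly different in a univariate fashion between classification groups, a multivariate logistic regression analysis will be performed". The last bullet of item 5 repeats that condition. Neither place lists the covariates, requires MELD or Child-Turcotte-Pugh (CTP) class, or says whether a non-significant primary marker would enter.

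The protocol itself links severity to each part of the comparison:

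- **AI**, item 2: "Prevalence of adrenal insufficiency (AI) in cirrhosis varies widely based on several factors, including severity of liver disease". Item 5 also plans to "Correlate higher MELD score with presence of adrenal insufficiency".
- **Spur cells**, Background: "Another abnormality well documented in cirrhotic patients, more frequently in patients with advanced disease, is spur cell anemia". Item 5 plans the matching MELD and CTP correlations.
- **Esterification**, item 5: "Correlate higher MELD score with deficiency in cholesterol esterification", with a parallel CTP aim.

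Item 3 describes the aim as "a pilot study to test for correlation between adrenal insufficiency, low serum cholesterol ester percentage, and spur cell anemia".

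**The concern.** If severity raises both the chance of AI and the chance of a marker, the two will be associated even when neither has anything to do with the other at a given severity. The MELD and CTP correlations in item 5 would reveal such an imbalance but would not remove it. The Background suggests that LCAT deficiency may account for part of the hepatoadrenal syndrome. A reader who wants to weigh that idea needs an estimate at comparable severity.

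Under the plan, whether that estimate exists depends on which p-values fall below 0.05. A single significant primary marker would not trigger the model. A triggered model might omit severity, or omit the marker. An estimate that appears only after significance also tends to be larger than the truth, by an amount that depends on a rule the plan does not give.

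**Working it through.** **Inputs from the plan.** 100 completers and 33% AI, so 0.33 × 100 = 33 with AI and 67 without; threshold 0.05. The plan gives no effect size, power or adjusted estimate, so it has no figure of its own to reproduce here.

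**Assumed inputs (not in the documents).** Severity odds ratio (OR) for AI 2.0 or 2.5 per SD; severity-marker correlation r of 0.3 or 0.5; marker prevalence 20%, 50% or 80%; two-sided tests.

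**Model.** Severity S is standard normal and MELD is taken to equal S. The marker is present when rS + √(1 − r²)·e exceeds the cut-off that gives the chosen prevalence. Then logit P(AI) = a + ln(severity OR)·S + ln(marker OR)·marker, with a set so that 33% have AI.

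**Step 1: crude against always adjusted, true adjusted OR of 1.** Percentage of studies with p<0.05, 4,000 simulations per cell, uncorrected chi-square; each cell shows crude / adjusted:

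| Prevalence | r 0.3, OR 2.0 | r 0.3, OR 2.5 | r 0.5, OR 2.0 | r 0.5, OR 2.5 |
|---|---|---|---|---|
| 20% | 10.3 / 4.6 | 14.2 / 4.4 | 21.1 / 4.3 | 29.0 / 4.6 |
| 50% | 11.2 / 4.5 | 14.3 / 4.5 | 21.2 / 4.6 | 31.3 / 4.9 |
| 80% | 8.5 / 3.9 | 9.9 / 3.8 | 14.4 / 3.8 | 22.4 / 3.2 |

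Across separate runs the ranges are about 8% to 33% crude and 2% to 6% adjusted. The median crude OR is 1.4 to 2.1. With a weaker severity effect (OR 1.5 per SD) the crude rate is about 7% to 11%.

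**Step 2: two entry rules that both fit item 2.** *Strict*: the model runs only if marker and MELD are both significant. *Loose*: any two of marker, MELD and CTP trigger it (CTP taken as two levels with latent correlation 0.8 to severity), and marker and MELD then enter.

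| | Strict | Loose | Always fitted |
|---|---|---|---|
| Median adjusted OR, true OR 1 | 1.6 to 3.4 | 1.0 to 1.1 | about 1.0 |
| Median adjusted OR, true OR 2 | 2.3 to 4.3 | 2.1 to 2.6 | 2.0 to 2.1 |
| No adjusted estimate, true OR 2 | 18% to 68% | 6% to 35% | none, apart from failed fits |

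For the strict rule the trigger is met in 0.316 to 0.815 of studies, and 1 − 0.815 = 0.185, 1 − 0.316 = 0.684.

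A separate simulation (marker prevalence 25%, two further severity-related factors, 3,000 replicates) gives the same pattern in geometric means. For a true OR of 2 it gives 2.7 to 3.8 if only significant factors enter, 2.43 to 2.68 if marker and severity are forced in once triggered, and 2.02 to 2.08 if always fitted.

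**Step 3: can the adjusted model be fitted?** Two parameters give 33/2 = 16.5 events per parameter; all seven variables listed in item 2 would give 33/7 = 4.7. Item 3, however, expects low esterification in nearly all cirrhotic patients. If 90% or 95% are deficient and there is no association at all, the chance that none of 33 AI patients is non-deficient is 0.90^33 = 0.031 or 0.95^33 = 0.184. With severity acting on both, simulation at 90% to 95% prevalence gives a zero cell in 8% to 43% of studies (true OR 1) or 19% to 61% (true OR 2). The ordinary odds ratio is not finite in those studies.

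**Step 4: cost in precision.** At 50% prevalence the median standard error of the log OR rises from 0.433 to 0.470 (ratio 1.09) at one end and from 0.438 to 0.507 (ratio 1.16) at the other. Power for a true adjusted OR of 2.0 is 5% to 31%.

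**The case against.** The strongest reply is that the study is a pilot that sets out to show association, and an unadjusted test does that. The explanatory role for LCAT is tentative Background, and nothing promises a severity-independent claim. This stands, and it is why the point is minor and the crude comparison should remain the primary description. A reader might infer that the crude comparison is invalid; the stated aim does not support that.

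A reader might also infer that every adjusted odds ratio from this plan would be biased away from 1. The documents do not support that either, because they do not say which terms enter. Under the loose rule a true OR of 1 gives a median of 1.0 to 1.1. In the separate simulation a true OR of 5 gives 5.5 to 6.2 with significant-only entry, against 5.2 to 5.4 always fitted. Selective availability survives; a fixed bias does not.

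Nor should one infer that the two-step procedure inflates type I error. Under the strict rule a marker significant both crudely and after adjustment occurs in only 0.6% to 2.9% of studies with no severity-independent link.

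Finally, adjustment may remove real signal. The Background cites esterification as a measure of the liver's synthetic capability, so it is partly a severity measure itself. That is a reason to report both estimates, not to leave the adjusted one to chance.

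**Conclusion.** The concern holds as a minor point. The primary comparison is unadjusted, the protocol's own statements make severity a foreseeable confounder, and the only adjusted model is conditional on significance with no stated covariates. A severity-adjusted estimate is therefore not guaranteed and is selectively available. With a true adjusted OR of 2 it would be missing in about 6% to 35% or 18% to 68% of studies, depending on how the trigger is read.

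The direction of these results follows from the protocol's expectations about severity. The sizes rest on assumed severity effects, correlations and prevalences, and on MELD capturing severity fully. If MELD is imperfect (reliability 0.7), the always-adjusted median for a true OR of 1 is 1.09 to 1.34, so some confounding would remain after the fix.

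**What to change.** Keep the unadjusted comparison as the primary description and delete the significance condition from items 2 and 5. Prespecify two logistic models, fitted whatever the univariate p-values and reported as odds ratios with 95% intervals beside the crude estimates:

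1. AI on cholesterol ester percentage (continuous) and MELD.
2. AI on spur cell anemia and MELD.

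If the binary esterification-deficiency term is used, fit it by penalised (Firth) logistic regression, because sparse cells are likely. Use CTP in place of MELD only as a sensitivity analysis. Item 2 says "Given that admitted patients to UVA are typically CTP B or C, we expect the incidence to be about 33" percent, so class is close to two levels, and adjusting for a two-level severity measure leaves a median OR of 1.12 to 1.47 when the truth is 1, against 0.98 to 1.03 for the continuous score. Label any wider model exploratory. Base any claim of a severity-independent link on the adjusted estimates, and note that residual confounding may remain.

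The cost is about one paragraph of text, with no new data or patients: MELD and ester percentage are already analysis variables. The price is a standard error roughly 9% to 16% larger and low power for the adjusted term, so the result should be read as an estimate with an interval, not a decisive test. Possible over-adjustment for esterification should be stated when the two estimates are reported together.

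### The conditional logistic model of adrenal insufficiency could have as few as 4 to 5 cases per coefficient, and the plan names no small-sample method

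*Combined protocol and SAP*

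**What the plan says.** Statistical Considerations, item 2, classifies patients by AI status and compares seven variables between the groups: MELD, CTP class, HDL, spur cell anemia, cholesterol ester percentage, cortisol binding globulin and free cortisol. The tests are t-tests and chi-square tests at p<0.05. If more than one factor differs, "a multivariate logistic regression analysis will be performed for adjusted analysis". The list of secondary analyses in item 5 ends with the same step: "Multivariate logistic regression if several variables are found to be significant".

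On numbers, item 2 states "we expect the incidence to be about 33" percent and plans 120 recruits, "assuming a 20% dropout rate to lead to 100 patients completing study protocol". Item 3 says "We feel 100 patients would be adequate to complete a pilot study" and argues that "this sample size would allow for adequate size comparator groups and decrease the likelihood of a Type II statistical error". It also says that the literature does not allow a formal power calculation.

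No item limits the number of terms, says how CTP is coded, says whether MELD and CTP may enter together, or names a penalised or exact method.

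**The concern.** What a logistic model can support depends on the size of the smaller outcome group, here the AI cases, and not on the total sample. With few cases per coefficient, ordinary maximum likelihood has two known weaknesses. Its log odds ratios are biased away from zero on average. It also has no finite estimate when a predictor separates the outcome completely or quasi-completely, for example through an empty cell.

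This model is the only adjusted analysis of AI in the plan. If most of the seven factors pass the screen, its odds ratios would tend to be somewhat too large and very imprecise, and a sparse binary or categorical term might not be estimable. The problem is one of estimation. It would remain even if the choice of variables were settled in advance.

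**Working it through.** **1. The plan's own figures.** 100 × (1 + 0.20) = 120 reproduces the stated recruitment, as does 100 + 20 with the 20 under Human Participants read as a count. Taken literally, a 20% loss from 120 leaves 120 × 0.80 = 96, and 100/0.80 = 125 would be needed. This matters little here, so both 100 and 96 are carried forward.

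**2. AI cases.** 100 × 0.33 = 33, or 96 × 0.33 = 31.7.

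**3. Coefficients.** Seven factors give 7 coefficients, or 8 if CTP enters as A/B/C. This is a ceiling, because only factors that pass the screen are candidates.

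**4. AI cases per coefficient.**

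| Coefficients | 100 completers | 96 completers |
|---|---|---|
| 2 | 16.5 | 15.8 |
| 3 | 11.0 | 10.6 |
| 4 | 8.3 | 7.9 |
| 7 | 4.7 | 4.5 |
| 8 | 4.1 | 4.0 |

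Item 2 says that AI prevalence varies widely. Over an assumed 20-50% of 100 completers, the range for 7-8 coefficients is 20/8 = 2.5 to 50/7 = 7.1.

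**5. Bias with all factors in the model.** The documents give no effect sizes, correlations or spur cell prevalence, so all of these are assumptions.
- Simulation A: n = 100, 33% AI, 1500 data sets per scenario, correlation 0.3 (MELD with CTP 0.7), spur cell odds ratio 3, other log odds ratios 0.2-0.4, spur cell prevalence 5-30%. The mean ordinary estimate for cholesterol ester, divided by the truth, was 1.10-1.21; with Firth it was 0.95-1.07. For spur cell at 10-30% prevalence the ratios were 1.03-1.19 and 0.95-1.02. At 5% prevalence the finite ordinary spur cell estimates were not inflated (0.73-0.88), and Firth gave 0.84-0.93.
- Simulation B: 7 coefficients, log odds ratios 0.4-0.6, correlation 0.3 or 0.5, 2000 data sets per scenario. For a true ester log odds ratio of 0.50, the ordinary mean was 0.57-0.60 (13-19% too large before rounding). Firth gave 0.50-0.53, with root-mean-square error 13-17% lower.

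**6. Bias against imprecision.** In simulation B the bias is 0.07-0.10. The standard error in comparable runs was about 0.34-0.43. In simulation A the median standard error of the spur cell log odds ratio was 0.55-0.96 at 10-30% prevalence.

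**7. Empty cells.** With spur cell prevalence p and no association, P(no spur cell patient in at least one AI group) = (1−p)^33 + (1−p)^67 − (1−p)^100.
- p = 5%: 0.184 + 0.032 − 0.006 = 0.210.
- p = 10%: 0.031 + 0.001 − 0.000 = 0.032.
- p = 15%: about 0.005.

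Across odds ratios of 1 to 5 the exact results are 16-23%, 1-4% and under 0.5%.

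**8. Non-estimable fits.** In simulation A with 7 coefficients these were 22-28% at 5% spur cell prevalence, 3.5-5% at 10%, and none at 20% or more. With CTP as A/B/C and class A assumed at 10% of patients, they were 23-62% overall and still 23-47% at spur cell prevalences of 20-30%. At those prevalences the 7-coefficient model never failed, so the cause is the sparse class A term.

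**9. With the p<0.05 screen applied** (simulation A, spur cell prevalence 10-20%), the median was 5-7 cases per term and all seven factors entered in 9-62% of data sets. Ordinary log odds ratios of selected terms were about 20-40% too large for spur cell and 20-85% for ester. Much of that comes from the selection itself.

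**The case against.** The strongest reply is that 7-8 coefficients is only the ceiling of a conditional secondary analysis. With two to four terms there are 16.5 to 8.3 cases per coefficient. With weaker assumed effects (six log odds ratios of 0.2, correlation 0.3) a median of four terms entered, and all seven entered in only 4-8% of samples. This stands: model size depends on unknown effects, and it is not certain that the odds ratios will be inflated. The case for Firth survives, because a further run in which the screen kept only about four terms still showed a root-mean-square error roughly 11-18% lower with Firth.

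It is also true that the bias is smaller than the standard error. Imprecision is the larger limitation, and no choice of fitting method removes it.

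A reader might infer that the spur cell result, part of the primary outcome, will be unusable. The documents do not support that. Item 4 defines the primary outcome as a two-group comparison, which this model does not touch. Loss of the adjusted term needs actual separation and a prevalence near 5%. The 5% in the Background is a spur cell burden within a patient, not a prevalence among patients. The Background says that spur cells are commoner in advanced disease, and item 2 expects mostly CTP B or C patients. The screen also lowers the failure rate at 5% prevalence (for example from 14% to 6% with weaker effects, or from 37% to 33% with strong ones).

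A reader might also take item 2's "Thus, 120 patients recruited should be sufficient to provide a statistical difference in our outcome measures of interest" or item 3's adequacy statement as covering the regression. Item 3 speaks of a pilot study of correlation and of comparator groups, and neither statement mentions the adjusted model.

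**Conclusion.** The point holds as a modest, inexpensive improvement to a conditional secondary analysis. From the plan's own figures, the model would rest on about 33 AI cases and could have as few as 4.1-4.7 per coefficient, with no small-sample method named. If most factors enter, the average inflation of ordinary log odds ratios is roughly 10-20%, below their standard errors. That size rests on assumed effects and correlations. Non-estimable terms are a real possibility only if spur cell anemia is rare, near 5%, or if CTP is fitted in three classes with few patients in class A. The documents give neither frequency.

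A fixed limit on the number of terms does not follow from this. Such a limit is a debatable rule of thumb, and it would need its own method for choosing among the screened factors.

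**What to change.** In Statistical Considerations, item 2, state that the adjusted model of AI will be fitted by Firth's penalised-likelihood logistic regression, with profile penalised-likelihood confidence intervals and tests. State also that it will be reported as exploratory, together with the observed number of AI cases and the number of coefficients fitted. Item 5 can refer back to this.

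The change needs wording and standard software, and no new patients or data. Its cost is slightly smaller odds ratios and a few significant adjusted terms fewer: about 4-7 percentage points for the ester term in the simulations, measured with Wald tests and not with the profile tests proposed here. Firth gives finite estimates under separation, but it does not correct the bias from the p<0.05 univariate screen, and the report should say so. The primary comparisons and item 3 need no change on this account.

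### CTP is planned only as a class, and the one named test suited to a class ignores order although every CTP aim is directional; CTP points, or a trend test on class, would use more of the severity information

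*Combined protocol and SAP*

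**What the plan says.** All references are to the combined protocol and SAP, Statistical Considerations.

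- Item 2, comparison by adrenal status: "Variables of interest for comparison between the groups include MELD score, Child-Turcotte-Pugh (CTP) classification" and several laboratory measures. No CTP point score is mentioned anywhere.
- Item 2, tests: "Student's t-test and Chi Square tests will be utilized to determine significance", and "a p-value <0.05 will be used as our threshold for significance". The tests are not assigned to variables, and sidedness is not stated.
- Item 2, correlations: after the list of MELD correlations, "similar correlate analysis will be done using CTP classification instead of MELD score". No coefficient or coding is given.
- Items 2 and 3, case mix: "admitted patients to UVA are typically CTP B or C". No percentages are given.
- Item 5, secondary aims: for example "Correlate higher CTP classification with presence of adrenal insufficiency" and "Correlate lower cortisol binding globulin levels with higher MELD score and CTP classification". Four aims name higher CTP class alone (AI, spur cells, HDL, esterification deficiency). Two more pair CTP with MELD (cortisol binding globulin, free cortisol).

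MELD, a numeric score, is planned for the same six associations.

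**The concern.** Two separate losses are possible.

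1. **Coarsening.** A class groups a graded point score. If nearly all patients are B or C, the class is close to a two-level split.
2. **Ignoring order.** A t-test needs a numeric variable or two groups, so chi-square is the named test that fits CTP class against a yes/no variable such as AI or spur cells. In its usual form it spends 2 degrees of freedom when three classes occur and takes no account of direction, whereas the aims are about a direction.

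Six of the 16 secondary associations use CTP. Because CTP sits beside MELD, a result that is significant for MELD but not for CTP could come from the coding alone and be read as a clinical difference. Item 2 also makes the multivariable model depend on univariate significance, so a weak univariate test could keep CTP out of it.

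**Working it through.** **Figures in the plan.** There is no power, effect size or correlation for any CTP analysis, so there is nothing to reproduce. From the documents I take 100 completers, about 33% with AI (33 against 67) and a 0.05 threshold, assumed two-sided.

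**Count of affected analyses.** Item 5 has 14 association bullets plus the regression bullet. Two of the 14 pair MELD with CTP, so 14 + 2 = 16 associations, of which 4 + 2 = 6 use CTP.

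**Assumptions not in the documents.** Points are whole numbers from 5 to 15, with class A up to 6, B 7–9 and C 10 or more. The point total is roughly normal with mean 9–10 and SD 1.5–2. In the logistic simulations below this gives 1–11% A, 36–49% B and 40–63% C, which fits a sample that is mainly B or C.

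**Step 1: coarsening alone, in closed form.** Cut a normal severity scale into classes scored 0, 1, 2. The share of the correlation kept is the sum of the normal densities at the cut points divided by the SD of the class score. Its square is the efficiency.

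- B and C only, 50/50: 0.399 / 0.5 = 0.798; squared, 0.64.
- B and C only, 80/20: 0.280 / 0.4 = 0.70; squared, 0.49.
- A/B/C of 5/50/45: (0.103 + 0.396) / √0.34 = 0.856; squared, 0.73.
- A/B/C of 20/50/30: 0.897; squared, 0.80.

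An ordered three-class analysis thus loses about 20–27% of the information, and a two-class one 36–51%, if the true relation is linear in the underlying scale.

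**Step 2: power for CTP against AI.** Simulation with n = 100, 33% AI and log-odds 0.5 per SD, over the point distributions above:

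| True shape of risk | Points | Trend test on class | Chi-square on class |
|---|---|---|---|
| Rises gradually with points | 60–62% | 43–50% | 33–39% |
| Steps by class | 43–50% | 56–59% | 44–47% |

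A second simulation fixed 33 against 67 patients and a mean difference of 0.5 SD in points. It gave 63–64% (points), 45–52% (trend) and 31–40% (chi-square). At 0.6 SD the figures were 78–80%, 59–67% and 44–54%. The closed-form t-test power at 0.5 SD is 65%, which agrees. With no true effect, rejection rates were about 4–6% for all three tests, so the differences are not bought with false positives.

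**Step 3: B and C only.** Trend and chi-square are then the same 1-df test. With a gradual rise at log-odds 0.5, power is about 46% with class against 61% with points. All of that loss is coarsening.

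**Step 4: CTP against a continuous marker.** With a true correlation of 0.3 and n = 100, power is about 82% with Spearman on points, 67–73% with ordered class and 60–66% with unordered class, across the point distributions tried.

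**The case against.** The strongest objection is that the plan never says CTP is unordered. A reader might infer this from the mention of chi-square, but the documents do not support it. The chi-square sentence assigns no test to any variable, the CTP sentence is about correlation, and all six aims in item 5 give a direction. This stands. Loss of order is implied only where chi-square would be applied to CTP class against a yes/no variable; for the continuous markers no method is named at all.

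Second, an advantage for points is partly built into any simulation in which risk is linear in points. This also stands. When risk steps by class, the trend test is best and points only roughly match chi-square. The documents do not say which shape is true.

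Third, the two losses do not add up freely. The 2-df penalty needs some class A patients, whereas the 64% efficiency figure belongs to an even B/C split with no A.

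Fourth, MELD already supplies a numeric severity measure for the same associations, the primary outcome does not use CTP, and item 3 calls the study a pilot. That limits the severity. It does not remove the point, because the plan tests CTP separately and will report it beside MELD.

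What survives is that an ordered test did better than chi-square in every three-class setting, and that points did better than class whenever severity was graded.

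**Conclusion.** The concern holds in a limited form. CTP is planned only as a class in a sample expected to be mainly B or C. The named test that suits a class does not match the directional aims, and the CTP correlations have no named method.

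For the AI comparison with three classes, ignoring order costs about 10–17 percentage points of power when severity is graded, and about 9–15 (56–59% against 44–47%) when risk steps by class. Coarsening to an ordered class costs roughly 10–19 points more, but only if the relation is graded. All these figures rest on the assumed point distribution and effect sizes.

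Three stronger conclusions are tempting and not supported: that the study will often miss real CTP gradients (this depends on an unknown shape and effect size), that about a third of the information is lost in general (this applies to an even two-class split), and that points would recover the loss at no cost whatever the truth.

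Severity is minor. This is a cheap improvement to secondary analyses.

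**What to change.** In Statistical Considerations, items 2 and 5:

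- Record the CTP point total and name it as the main CTP variable. Use a Welch t-test or logistic regression against AI and spur cells, and Spearman correlation against HDL, cholesterol ester percentage, cortisol binding globulin and free cortisol.
- Show class descriptively. Where class is tested, use a Cochran-Armitage trend test (yes/no variables) or Spearman (continuous markers) in place of unordered chi-square.
- State that tests are two-sided, if that is intended.

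The cost is a change of wording and one extra recorded item, with no more patients or blood tests. The documents do not say how CTP is derived; a class is normally assigned from its points, so the total should be available, but the study team should confirm this. The statistical price is that points are somewhat less powerful than a trend test on class if risk truly steps by class. The choice should therefore be fixed before the data are seen.
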